6.8 SAFETY ANALYSES

Safety analyses will be conducted using the safety analysis set 1 and safety analysis set 2. Only the safety data occurred in LTE14762 will be summarized unless specified otherwise.

Safety analysis under the original dose and regimen (i.e. before the 2020 voluntary dose pause) and the revised dose and regimen (i.e. after the 2020 voluntary dose pause) will be analyzed separately. The additional baseline prior to the revised dose regimen administration will be implemented for data collected under the revised dose and regimen. Similar descriptive summaries in reference to the additional baseline will be provided for laboratory, vital sign and ECG endpoints.

6.8.1 Study drug exposure

Duration of exposure (years) and the number of study drug doses used from Treatment Day 1 in the TDR14767(ALN-AT3SC-001)/LTE14762 under the original dose and regimen will be summarized descriptively, where duration of exposure (days) = date of the last dose of study drug – the date of the first significant dose of study drug + 28 days excluding the gaps between TDR14767(ALN-AT3SC-001)/LTE14762 and dose suspension in LTE14762. Duration of exposure and the number of study drug doses in LTE14762 study will be summarized similarly.

Duration of exposure under the revised dose and regimen will be summarized. If participant had the last dose under the Q2M dose frequency, the duration (days) = date of the last dose of fitusiran – the date of the first dose of fitusiran under the revised dose and regimen + 56 days. If participant had the last dose under the QM dose frequency, the duration (days) = date of the last dose of fitusiran – the date of the first dose of fitusiran under the revised dose and regimen + 28 days.

The overall duration of exposure regardless of revised dose from the first significant dose and/or from the first dose in the LTE14762 study until the end of study may also be summarized as needed. The planned dose intermittent period ([Table 4](#)) will be excluded from the overall duration of exposure.

Table 4 – Definition of planned dose intermittent periods

	Start date	End date	Note
Gap between parent and extension study	Last fitusiran dose date in parent study + 29 days	First fitusiran dose date in extension study – 1	If duration < 14 days, then no gap between the 2 studies.
2017 dose suspension	Last fitusiran dose before 01SEP2017 + 29 days	First fitusiran dose after 01SEP2017 – 1	If duration < 14 days, then no dose suspension period should be excluded.
2020 dose suspension	Last fitusiran dose date before 31Oct2020 + 29 days	First fitusiran dose after 26Jan2021 – 1	If duration < 14 days, then no dose suspension period should be excluded

Note: Duration is calculated as end date – start date +1 for each dose intermittent periods.

6.8.2 Adverse events

Adverse events (AE) analysis will include treatment-emergent events, with onset occurring in the LTE14762 study. (Note: All AEs collected in LTE14762 are considered TEAE because all participants received dose in TDR14767(ALN-AT3SC-001).)

All AEs will be coded using the MedDRA(version 25.1 or later) coding system and displayed in tables and data listings using system organ class (SOC) and preferred term (PT). AEs will be summarized by the numbers and percentages of participants reporting at least 1 AE, having at least 1 AE by primary SOC and PT. A participant with multiple occurrences of an AE will be counted only once in the respective AE category. Participants who report multiple occurrences of the same AE (preferred term) will be classified according to the most related or most severe occurrence, respectively.

All AE summaries will be summarized (frequency counts and percentages) by system organ class and/or preferred term, unless specified otherwise. The SOC will be presented according to

international standards (MedDRA Internationally Agreed Order), and the preferred term will be sorted within each SOC in decreasing order of frequency.

The following events are considered to be AEs of special interest (AESI):

1. ALT or AST elevations $>3 \times$ ULN
2. Suspected or confirmed thromboembolic events
3. Severe or serious injection site reactions (ISRs), ISRs that are associated with a recall phenomenon (reaction at the site of a prior injection with subsequent injections) or, those that lead to temporary dose interruption or permanent discontinuation of study drug.
4. Systemic (injection associated reactions (IARs), defined as hypersensitivity reactions which are related or possibly related to IMP.
5. Cholecystitis
6. Cholelithiasis

The identification of cholecystitis and cholelithiasis will be a combination of systematic search of higher level group term (HLGT) and AESI collected as it is in CRF. AEs whose HLT fall into the categories listed below will be considered as AESI of cholecystitis and cholelithiasis:

1. Bile duct disorders,
2. Gallbladder disorders
3. Hepatic and hepatobiliary disorders

An overall summary of TEAEs will include the number and percentage of participants with any TEAE, any TEAE assessed by the Investigator as related to study drug (possibly related or definitely related), any serious TEAE (TESAE), any TESAE related to study drug, any TEAE of special interest; any AE/SAE leading to permanent study drug discontinuation, any TEAE/TESAE leading to study withdrawal, and any deaths. The TEAE onset within any major surgery period will be provided in a separate column in the overview summary statistics as well as in the overall column. They will be excluded from the rest of by-indication columns in the table.

Tabulations of TEAEs by SOC and PT excluding those AE onsets within major surgery period will be produced for the following:

1. TEAEs
2. TEAEs by severity
3. Treatment emergent SAEs
4. TEAEs related to study drug
5. Treatment emergent SAEs related to study drug
6. TEAEs leading to permanent study drug discontinuation
7. Treatment emergent SAEs leading to permanent study drug discontinuation
8. TEAEs leading to study withdrawal
9. Treatment emergent SAEs leading to study withdrawal
10. Treatment emergent AESI (Adverse Events of Special Interest)
11. TEAEs potentially consistent with Covid-19. These AEs will be identified based on SMQ group searching.

All AEs will be listed along with the information collected on those AEs, eg, AE relationship to study drug, AE outcome etc. By-participant listings will also be provided for the following: all participant deaths, all SAEs, and all AEs leading to permanent study drug discontinuation or study withdrawal, all AEs leading to death. AE onset during the major surgery period will also be included in each of the by-participant listing with major surgery flag.

The incidence rate of severe or serious ISRs will also be summarized. The incidence rate is defined as the number of severe or serious ISRs per study drug injection. If multiple ISRs occur between two consecutive injections, they will be counted under the first injection as 1 ISR.

Because of hepatitis C infected participant got enrolled in the TDR14767(ALN-AT3SC-001) study, participants with treatment emergent ALT or AST elevations > 3 ULN AESI will be analyzed based on their HCV status at the enrollment of LTE14762 study.

Additional summary of incidence rate for TEAE, SAE, AEs leading to permanent study drug discontinuation and AESI before and after the 2020 dose pause by primary SOC and PT will be provided.

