9.2.7 Adverse Events of Special Interest

The following events are considered to be AEs of special interest (AESI):

- ALT or AST elevations >3× ULN
- Suspected or confirmed thrombosis
- Severe or serious ISRs; ISRs that are associated with a recall phenomenon (reaction at the site of a prior injection with subsequent injections), or those that lead to temporary dose interruption or permanent discontinuation of fitusiran

- Systemic injection associated reactions (IARs), defined as hypersensitivity reactions which are related or possibly related to IMP.
- Cholecystitis*
- Cholelithiasis*

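### SAP 6.8.2 counts every adverse event in three MedDRA groups, one of them hepatic, as a cholecystitis or cholelithiasis event of special interest, with no term list or review of hits

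*SAP*

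**What the plan says.** Protocol 9.2.7 lists the AESIs. "Cholecystitis" and cholelithiasis are two of them, and ALT or AST above 3× ULN is a separate one. SAP 6.8.2 repeats the list, with the two biliary conditions as items 5 and 6.

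The SAP then says how the two conditions are to be found: by "a combination of systematic search of higher level group term (HLGT) and AESI collected as it is in CRF". The operative sentence follows: "AEs whose HLT fall into the categories listed below will be considered as AESI of cholecystitis and cholelithiasis". Three groups are listed: bile duct disorders, gallbladder disorders, and "Hepatic and hepatobiliary disorders".

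Three planned outputs in the same section use the AESI class:
- the overview of TEAEs, which has a row for "any TEAE of special interest";
- the AESI tabulation, introduced by "Tabulations of TEAEs by SOC and PT excluding those AE onsets within major surgery period will be produced for the following";
- an incidence summary by SOC and PT that covers "AEs leading to permanent study drug discontinuation and AESI before and after the 2020 dose pause".

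SAP 2.6 gives alignment with other fitusiran studies as the reason for adding the algorithm.

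**The concern.** The AESI is two named conditions, but the rule that populates it is wider. By its own name the third group covers hepatic disorders, and belonging to a group is enough to be classed as a cholecystitis or cholelithiasis event. A hepatic event with no gallbladder or bile duct component would therefore carry a biliary label.

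The same section words its other broad search more carefully. Item 11 of the tabulations reads "TEAEs potentially consistent with Covid-19. These AEs will be identified based on SMQ group searching", so those hits are presented as possible cases, whereas the biliary search declares cases.

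Long-term safety is the primary objective. The rationale for Amendment 07 (Protocol 18.6.7) describes cholecystitis and symptomatic cholelithiasis as newly identified risks, and Protocol 9.1.7.2 asks for extra work-up when a gallbladder is removed. A count that mixes hepatic events into this class blurs the signal that those additions were meant to clarify.

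**Working it through.** The plan gives no event counts and no figure to reproduce. The check is a comparison of text, followed by one small calculation.

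**1. Definition against rule.** Take a non-biliary hepatic AE that is not an ALT or AST elevation above 3× ULN.
- Protocol 9.2.7, and the list in SAP 6.8.2: not an AESI on the liver or biliary items.
- SAP 6.8.2 search rule: an AESI of cholecystitis and cholelithiasis, because it falls in the third group.

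This rests on the group's name. The documents do not give the MedDRA contents of the group.

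**2. Is there a restriction elsewhere?** SAP 6.8.2 gives no preferred-term list, exclusion or review of hits, and SAP 2.6 only points back to 6.8.2. Where the SAP intends human review it says so: protocol violations are manually adjudicated (Section 4), and unlisted antithrombin treatments go to the medical team (Section 6.4, Table 3 footnote b).

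**3. Could the reference to the CRF narrow the rule?** If the combination meant an intersection, only events flagged by the investigator would qualify. The next sentence makes group membership sufficient, so this reading fails.

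**4. Can such events occur?**
- Against: exclusion criterion 1 (Protocol 4.2) removes clinically significant cirrhosis, ALT or AST above 3× ULN at screening, and hepatitis C currently needing ribavirin or interferon.
- For: SAP 6.8.2 records that participants with hepatitis C entered the parent study, and Protocol 9.2.1 makes a pre-existing condition that worsens after the first dose a reportable AE.

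The number is therefore unknown, and zero is possible.

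**5. Which outputs change?**
- AESI tabulation and before/after-pause summary: the event is added under its own SOC and PT. SAP 6.8.2 also says AEs are summarized by participants with at least one event, so the AESI table may carry a total that changes.
- Overview row: it changes only for a participant with no other AESI. Someone with ALT or AST above 3× ULN is already counted.
- Onset in a major surgery period: such an event counts in the overall column of the overview and in a separate surgery column. It is left out of the by-indication columns and of the SOC/PT tabulations.

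**6. Size of one step in the overview row, overall column.** Step = 1/n, where n is the size of the safety analysis set.
- Upper limit on n: 48 (Protocol 10.1). Smallest step = 1/48 = 2.1 points.
- Protocol 1.3.3 reports 13 patients at 50 mg and 21 at 80 mg in this study as of August 2017. If the groups do not overlap, Safety Analysis Set 1 has at least 13 + 21 = 34 participants, and the largest step is 1/34 = 2.9 points.
- Set 1 range on that assumption: 2.1 to 2.9 points per affected participant.
- Set 2: at least 2.1 points. The documents give no lower limit on n, so no upper limit on the step.
- No affected participants: 0.

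**The case against.** The strongest reply is that the breadth is deliberate. For a newly identified risk a sensitive search is sensible, SAP 2.6 says the algorithm matches other fitusiran studies, and a narrow list could miss a biliary event coded to a neighbouring term. This stands as a reason to keep the search. It does not justify calling every hit a case, and a separate, accurately labelled table keeps both the sensitivity and the comparison.

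A second reply is that the practical effect is small. All TEAEs are tabulated by SOC and PT and all AEs are listed, so cholecystitis and cholelithiasis can be read off directly. No pooled cholecystitis/cholelithiasis percentage is planned. The error adds events and does not remove any, and investigator reporting of AESIs does not depend on the SAP search. All of this stands and limits the severity.

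A reader might also infer that the search cannot be programmed, because the SAP names HLGT in one sentence and HLT in the next. The documents do not support that as a defect in its own right. The listed categories can be read as group terms into which an event's HLT falls, which is one consistent HLGT search. The abbreviation list defines only the group term (with its letters transposed) and has no entry for HLT, so a slip is the other likely explanation.

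**Conclusion.** The rule as written misclassifies any non-biliary hepatic AE as a biliary AESI, and nothing in either document corrects it. The severity is minor. The effect is confined to AESI classification and descriptive safety counts, and it may be nil. Where it occurs, each affected participant with no other AESI moves the overview row by at least 2.1 points in the overall column. For Set 1 the step is 2.1 to 2.9 points, assuming that the two dose groups in Protocol 1.3.3 do not overlap.

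The conclusion assumes that the third group contains hepatic terms that are not biliary, as its name says. A reader might go further and infer that the trial will materially overstate biliary risk. That cannot be shown, because no event counts are given and individual terms remain visible.

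**What to change.** Before database lock, amend the paragraph in SAP 6.8.2 as follows:

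1. Count as cholecystitis or cholelithiasis AESIs only the CRF-reported AESIs plus search hits that match a pre-specified list of cholecystitis and cholelithiasis terms. Say explicitly that the two sources are joined as a union.
2. Do not assign hits from the hepatic and hepatobiliary group on group membership alone.
3. Keep the three-group search as a separate table labelled *hepatobiliary events (broad search)*.
4. In the same edit, use one MedDRA level name throughout.

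The ALT/AST AESI stays as it is. The cost is one paragraph, a short term list and one extra table, with no new data. The narrower AESI count will not be directly comparable with other fitusiran studies that use the broad search; the separate table covers that comparison.

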10.2.6 Safety Analyses

Adverse events will be summarized by the MedDRA System Organ Class and Preferred Term. Incidence of treatment-emergent adverse events (TEAEs; those events that started after exposure to study drug or worsened in severity after dosing) will be presented by dose level and overall. Incidence of TEAEs will also be presented by maximum severity and relationship to study medication or underlying hemophilia. The incidence of SAEs and AEs leading to discontinuation of treatment will also be tabulated. By-patient listings will be provided for deaths, SAEs, and events leading to discontinuation of treatment.

Descriptive statistics will be provided for clinical laboratory data (including biochemistry, hematology, urinalysis, and coagulation) and vital signs data, presented as both actual values and changes from baseline relative to each on-study evaluation. Laboratory shift tables from baseline to worst values will be presented. Baseline will be defined as the last observation on or before Day 1. Abnormal physical examination findings, 12-lead ECG data, and antidrug antibody results will be presented in a by-patient data listing. Antidrug antibody results will also be tabulated.

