2.7 MODIFICATION MADE IN SAP TO THE STATISTICAL SECTION IN PROTOCOL

Description in SAP	Rationale	Description in Protocol
The analysis periods are defined in Section 6.3. The start of analysis periods is the date of fitusiran with at least 20mg since parent study entry.	Prior exposure on fitusiran in TDR14767(ALN-AT3SC-001) may impact the efficacy evaluation in LTE14762. The analysis will incorporate the parent study data and extension study data for a comprehensive assessment of efficacy on bleeding.	Annualized bleed rate estimate will be calculated as the number of bleed events occurring 4 weeks after the first dose of fitusiran in this study and until the End of Study visit.

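### SAP 6.8.2 leaves adverse events with onset in a major-surgery period out of all 11 numbered SOC/PT tables, so no planned table shows their severity or relatedness by term

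*SAP*

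**What the plan says.** SAP 6.8.2 opens with a general rule that does not mention surgery: "Adverse events (AE) analysis will include treatment-emergent events, with onset occurring in the LTE14762 study". Its list of events of special interest has as item 2 "Suspected or confirmed thromboembolic events".

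The section then plans four kinds of output, with different treatment of events starting in a major-surgery period:

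- **Overview table.** These events "will be provided in a separate column in the overview summary statistics as well as in the overall column". They are left out of the by-indication columns.
- **Numbered tables.** "Tabulations of TEAEs by SOC and PT excluding those AE onsets within major surgery period will be produced for the following": a list of 11 items follows.
- **Listings.** "AE onset during the major surgery period will also be included in each of the by-participant listing with major surgery flag".
- **Un-numbered summary by SOC and PT.** "Additional summary of incidence rate for TEAE, SAE, AEs leading to permanent study drug discontinuation and AESI before and after the 2020 dose pause". Nothing is said about surgery.

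Protocol 10.2.6 summarizes adverse events by SOC and PT, tabulates serious events and events leading to discontinuation, and adds: "Incidence of TEAEs will also be presented by maximum severity and relationship to study medication or underlying hemophilia". It makes no exception for surgery. SAP 2.7, where the SAP records its changes to the protocol's statistical section, has one entry, on efficacy analysis periods: "The start of analysis periods is the date of fitusiran with at least 20mg since parent study entry". SAP 2.6, on other SAP changes, does not mention the surgery exclusion either.

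**The concern.** Long-term safety and tolerability is the primary objective. Thrombosis is the risk that led to the revised dose and regimen (protocol 1.5). Protocol 1.6 adds that concomitant factor or bypassing agent, used for breakthrough bleeds, may raise that risk. Major surgery is a time when such products are given, so it is a window in which a safety reader would look for thrombosis by term.

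Under the rule as written, a thrombosis starting in that window would be absent from the numbered serious-event and special-interest tables. A reader would have to combine the overview counts with the flagged listings, or rely on a summary whose handling of these events is not stated.

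The exploratory objective includes perioperative safety. SAP 4 says the operative procedure analysis sets will be used to assess safety as well as hemostatic efficacy. SAP 6.6 then plans only hemostatic ratings and possible narratives. For concomitant medication, SAP 6.8.7 makes the same surgery-period exclusion but adds a separate surgery-period summary. Adverse events have no such companion by term.

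**Working it through.** There is no figure to reproduce. The check is a count of tables and a comparison of outputs.

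**Step 1: numbered tables under the exclusion.** The items are (1) TEAEs, (2) by severity, (3) SAEs, (4) related TEAEs, (5) related SAEs, (6) TEAEs leading to drug discontinuation, (7) SAEs leading to drug discontinuation, (8) TEAEs leading to withdrawal, (9) SAEs leading to withdrawal, (10) AESI, (11) COVID-19-type events. All 11 sit under one heading and none is exempted.

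**Step 2: where an event starting in the major-surgery period would appear.**

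| Output | Included? | By SOC/PT? | Severity? | Relatedness? |
|---|---|---|---|---|
| Overview, surgery and overall columns | Yes | No | No | Yes, as a count |
| Overview, by-indication columns | No | – | – | – |
| 11 numbered tables | No | – | – | – |
| Incidence-rate summary before/after the 2020 pause | Not stated; probably yes under the general rule | Yes | No | No |
| Flagged listings | Yes | By event | By event | By event |
| SAP 6.6 surgical cases | Optional narrative | No | No | No |

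The listing row assumes that severity is among the collected items listed; SAP 6.8.2 names relationship and outcome as examples.

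**Step 3: what the incidence-rate summary could cover.** It names TEAE (1), SAE (3), discontinuation (6) and AESI (10), which is 4 categories. The remainder is 11 − 4 = 7: severity (2), related TEAEs (4), three serious subsets (5, 7, 9), withdrawal (8) and COVID-19 (11).

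**Step 4: what the protocol asks for.** Protocol 10.2.6 asks for five of these categories: TEAE, severity, relatedness, SAE and discontinuation. On the plain reading, the incidence-rate summary gives TEAE, SAE and discontinuation by term. That leaves 5 − 3 = 2, severity and relatedness. Relatedness is counted in the overview without terms; severity is not in the overview at all.

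**Step 5: which events are affected.** SAP 6.8.2 does not define the period or point to a definition. Protocol 5.7 and SAP 6.3 run it from the day of surgery to the last day of supplemental hemostatic or antithrombotic treatment under the perioperative plan, with no fixed maximum. An event after minor surgery, or starting after that last day, therefore stays in the numbered tables. Protocol 18.2.1 counts extraction of any molar tooth as major surgery, so the rule reaches beyond large operations.

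**The case against.** The strongest reply is that nothing is hidden. The overview gives surgery-period events their own column and keeps them in the overall column. The listings flag each one, and with at most 48 patients the listings can be read. The exclusion appears only in the sentence heading the list of 11. The incidence-rate summary is outside that list and is governed by the general rule, so a thrombosis would probably appear there by term as a TEAE and an AESI, and as an SAE if serious. This stands, and it limits the point.

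Separate presentation also has a rationale. Around major surgery, protocol 5.7 calls for fitusiran doses to be withheld and provides for extra hemostatic treatment and possible antithrombin replacement, so attribution to fitusiran is confounded. That supports showing these events separately. It does not support leaving them out of the main tables by term without a by-term counterpart, which is what SAP 6.8.7 provides for medication.

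Protocol 5.7 recommends postponing non-urgent major surgery until after the trial, so few cases may arise. That bears on size, not on whether the tables meet the protocol.

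Three stronger readings are tempting and fail. One is that a perioperative thrombosis would go unreported, or would appear in no table by term; the overview, the listings and probably the incidence-rate summary contradict this. Another is that seven of the 11 categories represent missing required tables. Five of those seven are serious subsets, withdrawal tables or the COVID-19 table, none of which protocol 10.2.6 requests. The third is that all perioperative events are excluded; those around minor surgery are not.

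**Conclusion.** The point holds in a limited form. The SAP applies to all 11 numbered SOC/PT tables an exclusion that the protocol does not contain and that SAP 2.6 and 2.7 do not record.

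Two gaps are firm whichever way the incidence-rate summary is read. No planned table shows the severity or relatedness of these events by term, although the protocol asks for TEAE incidence by both. And no adverse-event summary by term exists for the surgery period, although SAP 4 assigns perioperative safety to the operative procedure sets.

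For TEAE, SAE, discontinuation and AESI by term, the gap depends on one unstated rule. It closes if the incidence-rate summary includes these events, which is the plain reading but is an inference from the general rule.

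The effect on reported incidences cannot be estimated, because neither document gives a number of major surgeries or of events within them. This is a reporting weakness worth correcting because safety is the primary objective and thrombosis the leading risk. It is not evidence that any result would be wrong.

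**What to change.** In SAP 6.8.2:

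1. Add a SOC/PT column or table, with severity and relatedness, for TEAEs, SAEs and AESI with onset in the major-surgery period.
2. Include these events in the overall column of the TEAE, severity, related-event, SAE and AESI tables, and keep the surgery-excluded columns beside them.
3. State that the incidence-rate summary before and after the 2020 pause includes them.
4. Cross-reference the definition of the major-surgery period.

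Record in SAP 2.7 any exclusion that remains, with its reason.

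The cost is SAP wording and a few extra outputs, with no new data. The downside is that overall incidences will contain some events caused by the surgery rather than by fitusiran; the separate column identifies them.
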